### 14.2.2 Delta-Based Controlled Imputation (Tipping point)

A delta-based controlled imputation approach using the tipping point analysis will be performed as a sensitivity analysis of treatment superiority, if shown. Tipping point analysis will assess how departures from MAR assumption must be to overturn conclusions from the primary superiority analysis. Tipping point will be based on iterative application of MI.

In case of death or re-transplantation events, FEV1 will be imputed as zero at each nominal day post event.

In the first iteration, the missing FEV1 outcomes will be imputed separately for each treatment group, using the fully conditional specification. The imputation model will include baseline FEV1, age, region, use of azithromycin at randomization, and intermediate FEV1 up to week 48 as covariates. Two hundred data sets will be generated, and the random seed number will be 99823. Non-missing values from all patients will be used.

In successive iterations, to represent departures from MAR, values  $\Delta 1$  and  $\Delta 2$  will be added and subtracted to the imputed values for L-CsA plus SoC treatment and SOC treatment groups respectively.  $\Delta 1$  and  $\Delta 2$  will range from 0 to 100 mL (0.1 L) by 10 mL (0.01 L).

For each scenario (i.e., each combination of  $\Delta 1$  and  $\Delta 2$ ), the 200 delta-adjusted imputed datasets will be analyzed using the primary LMM including all observed and imputed data. Rubin's rule will be used for combining results to draw inference. The adjusted difference between treatment groups in mean FEV1 change from baseline after 48 weeks will be provided along with its p-value for the null hypothesis of no difference.

These results will show how extreme the departures from MAR must be to overturn the results of the primary analysis. Controlled imputation is always feasible, independent from the incidence of dropouts.

The core excerpt of code for this sensitivity analysis is reported in section 17.3.

## 14.2.3 Mixed model repeated measures (MMRM)

To investigate robustness against deviations from the model, a MMRM model will be carried out using all observed available FEV1 measurements (under MAR assumption). The dependent variables are the absolute change from baseline of FEV1 measurements at visit 2 (i.e., the first post-baseline visit) through visit 9 (Week 48). In case of death or re-transplantation events, FEV1 will be imputed as zero at each nominal day post event.

As fixed effects, the model will contain the following covariates (except from the intercept): categorical (scheduled) visit, treatment, the interactions of treatment by categorical visit, baseline  $FEV_1$ , the interactions of categorical visit with the baseline  $FEV_1$ , region (North America versus all other countries together), age (< 55 versus  $\geq$  55 years), and use of azithromycin at

Final Version 5.0 Page 44 of 76

randomization (i.e. Baseline, Visit 1). Random effects per patient for this model will include categorical visit.

An unstructured covariance pattern will be used to estimate the variance—covariance of the withinpatient repeated measures. If the model fails to converge, a heterogeneous Toeplitz structure will be used. Parameters will be estimated using REML with the Newton—Raphson algorithm and using the Kenward—Roger method for calculating the denominator degrees of freedom.

Treatment group comparisons at each visit will be estimated by differences between least squares (LS) means from the visit by treatment interaction, with accompanying p-values and 95% CIs. The robustness of primary results will be evaluated by means of the difference of LS means at week 48.

The core excerpt of code for the sensitivity analysis is reported in section 17.4.

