#### 9.4 Visit Windows

Following randomization, the visits are scheduled every 4-8 weeks, but the actual times of the visits may deviate from the scheduled times. With spirometry data, consideration needs to be taken to remove the rejected spirometry assessments for analysis before applying the visit windowing.

To allow for any presentation that summarizes values by visit, visit windows will be defined according to the table below. Measurements (both scheduled and unscheduled) will be allocated to visits (and analyzed) as reported in Table 2.

Table 2: Visit windows.

Nominal Visit	V1	V2	V3	V4	V5	V6	V7	V8	V9/EoT	V10/EoS
Nominal Week	W0	W4	W8	W12	W16	W24	W32	W40	W48	W52
Nominal Day	1	29	57	85	113	169	225	281	337	365
Time (days) from	0	1-42	43-70	71-98	99-140	141-196	197-252	253-308	*309-364	*365-385
Randomization***	U	1-42	43-70	/1-98	99-140	141-190	197-232	233-308	**309-385	. 202-282

\*Patients who do not consent or participate in BT-L-CsA-303-FU (BOSTON-3).

Data collected after 385 days or 364 days (as applicable, as per the table above) will not be used for analyses but will be included in the listings. If there are two or more measurements assigned to a nominal visit, only the one closest to the scheduled time of the visit will be used in the analysis, unless an additional measurement will be the last measurement during a patient's trial participation

Final Version 5.0 Page 29 of 76

\*\*Patients who consented and participated in BT-L-CsA-303-FU (BOSTON-3) and will not have a V10 / EoS

\*\*\* Visit windows are based on [visit date – date of randomization visit] formula for time (days) from randomization.

(e.g., in case of an unscheduled visit before premature withdrawal), which will always be included into the analysis.

In the case a scheduled visit is performed in the same date of an unscheduled visit, the scheduled visit assessments will be used; in the specific case of spirometries, if the spirometry data is accepted in the scheduled visit, the scheduled visit data will be used, otherwise (if the spirometry in the scheduled visit is rejected) if the spirometry data is accepted in the unscheduled visit, the unscheduled visit data will be used.

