#### 14.2.4 MMRM under MNAR

Each of the 200 imputed datasets created under MNAR condition as described in section 14.2.1, will be analyzed using the MMRM described in previous section 14.2.3 including all observed and imputed data. Rubin's rule will be used for combining results to draw inference.

Treatment group comparisons at each visit will be estimated by differences between least squares (LS) means from the visit by treatment interaction, with accompanying p-values and 95% CIs. The robustness of primary results will be evaluated by means of the difference of LS means at week 48.

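### As worded, the MMRM sensitivity model puts random visit effects on top of an unstructured covariance over the same visits, so only their sum can be estimated

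*SAP*

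**What the plan says.** SAP 14.2.3 sets up the MMRM as a check of the primary LMM against departures from its model. The outcome is change from baseline in FEV1 at visits 2 to 9, which is eight repeated measures. After the fixed effects, two consecutive statements describe the covariance:

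- "Random effects per patient for this model will include categorical visit".
- "An unstructured covariance pattern will be used to estimate the" variances and covariances of the repeated measures within a patient.

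The covariance type of the random effects is not given. Nothing says that one statement replaces the other. The fallback is: "If the model fails to converge, a heterogeneous Toeplitz structure will be used". It does not say that the random visit effects are dropped at that point. Estimation is by REML with Newton-Raphson and Kenward-Roger degrees of freedom.

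SAP 14.2.4 carries the model over: each of the 200 imputed data sets "will be analyzed using the MMRM described in previous section 14.2.3 including all observed and imputed data", with results pooled by Rubin's rule. It does not say how the fallback works across imputations.

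SAP 9.4 gives the general rule for several measurements in one window: "only the one closest to the scheduled time of the visit will be used in the analysis". The exception is a last additional measurement, which is always kept. The code is said to be in section 17.4, but the public copy shows only that heading.

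**The concern.** A random effect for each visit and an unstructured residual covariance indexed by visit describe the same thing twice. An MMRM normally carries one of them. With both, the model has more covariance parameters than the data can determine, at any sample size.

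At stake is the conduct of two planned robustness checks, not the primary result. An over-parameterised model can stop without converging, or can converge with a covariance matrix that is not positive definite. The first outcome sends the analysis to a more restrictive structure for a reason unrelated to the data. The second has no rule in 14.2.3, although SAP 14.1.5 does provide one for the primary LMM. Kenward-Roger also needs the covariance matrix of the variance parameters, and that does not exist when the information matrix is singular. In 14.2.4, if some imputed data sets triggered the fallback and others did not, Rubin's rule would pool results from different covariance models.

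**Working it through.** **The plan's own count.** SAP 14.1.5 states 11 covariance parameters for the primary LMM. Four random effects with an unstructured matrix give 4 × 5 / 2 = 10; adding one residual variance gives 11. This reproduces. The SAP gives no count for the MMRM.

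**Algebra.** Let G be the covariance of the random visit effects, R the within-patient residual covariance, and A the matrix that picks out a patient's observed visits. Both layers are indexed by visit, so the patient's covariance is V = AGA' + ARA' = A(G + R)A'. Any symmetric matrix can be moved from G to R without changing V.

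**Counts for m = 8 visits.** Unstructured: 8 × 9 / 2 = 36. Heterogeneous Toeplitz: 8 variances + 7 correlations = 15. No model for V can have more than 36 estimable covariance parameters. The rank is that of the Jacobian of the distinct elements of V with respect to the parameters, found numerically.

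| Reading | Parameters | Rank |
|---|---|---|
| Unstructured R only | 36 | 36 |
| Unstructured G + unstructured R | 36 + 36 = 72 | 36 |
| Single variance component G + unstructured R | 1 + 36 = 37 | 36 |
| Unstructured G + independent residual | 36 + 1 = 37 | 36 |
| Fallback: unstructured G + heterogeneous Toeplitz R | 36 + 15 = 51 | 36 |
| Fallback: single variance component G + heterogeneous Toeplitz R | 1 + 15 = 16 | 16 |
| Heterogeneous Toeplitz R only | 15 | 15 |

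Every reading tested that keeps a separate random visit layer before the fallback is over-parameterised. The fallback cures this if G is a single variance component, but not if G is unstructured.

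**What a fit does.** One trial was simulated with 169 patients (the number randomized, SAP 8.2) and eight visits. The covariance and missingness were assumed, because the documents give neither. REML was maximised by a ridge-stabilised scoring algorithm.

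| | Unstructured R only | G + R, start 1 | G + R, start 2 |
|---|---|---|---|
| Iterations | 11 | 11 | 11 |
| −2 REML log-likelihood | −2651.1976 | −2651.1976 | −2651.1976 |
| Week 48 difference (L) | 0.1561 | 0.1561 | 0.1561 |
| Model-based SE (L) | 0.0551 | 0.0551 | 0.0551 |
| Information rank | 36 of 36 | 36 of 72 | 36 of 72 |
| Week 48 variance, G part + R part | 0 + 0.1096 | 0.0248 + 0.0848 | 0.1698 − 0.0602 |

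The Week 48 variance sums to 0.1096 in all three columns, so the total is fixed and the split depends on the starting values. From start 1, G was not positive definite; from start 2, R was not. The ridge helps convergence, so this run shows that the redundant model can converge. It does not show that Newton-Raphson in the trial's software would.

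**The case against.** The strongest reply is that the two statements may loosely describe a single unstructured repeated-measures covariance, and that the code in 17.4 may fit exactly that. The public copy cannot settle this. That stands, and it limits the point to the prose. It does not remove it: if the code fits one covariance, the random-effects sentence misdescribes the analysis; if the code follows the prose, the model is not identified.

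Three stronger readings are tempting, and the documents do not support them.

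- A reader might infer that the treatment estimate is arbitrary. It is not. Robustness is judged on the Week 48 difference in LS means, which depends on G + R and not on the split.
- A reader might infer that the specification itself forces the fallback. The stated trigger is failure to converge. Redundancy makes that more likely, but the result depends on software and starting values, and the simulated fit converged.
- A reader might infer that 36 − 15 = 21 covariance parameters are lost. That holds only if the random visit effects are gone at the fallback, and the text does not drop them. If an unstructured G stays, V is still fully unstructured and nothing is lost.

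It is also fair to say that heterogeneous Toeplitz leaves all eight variances free and restricts only the correlations, so the cost of an unneeded switch is not shown to be large. Nor has it been shown that convergence would in fact differ between imputations.

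The exception in SAP 9.4 for a last extra measurement does not rescue the text. Two records in one window would use the same row of both G and a visit-indexed unstructured R, so only the sum still enters, and two identical rows would make V singular.

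**Conclusion.** The covariance statement in 14.2.3 is wrong as worded, and the consequence is small. The excess is 36 parameters if G is unstructured (72 against 36) and 1 if it is a single variance component (37 against 36). The practical effects are a raised but unquantified chance of non-convergence or a non-positive-definite matrix, an undefined basis for the Kenward-Roger adjustment, and a fallback that may not be identified either.

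The ranks assume one record per patient and visit and a residual covariance indexed by the same visits as the random effects. The equality of the estimate and model-based SE with those of a standard unstructured MMRM holds when the fit reaches its maximum; Kenward-Roger quantities could still depend on how the software handles the singularity.

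Only 14.2.3 and 14.2.4 are touched. The primary LMM has its own random-effects structure, and the MMRM is not named in the visible text of the testing order in SAP 8.4. Other sensitivity analyses (MNAR imputation, tipping point, ANCOVA, selection and joint models) do not use this model. Severity: minor.

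**What to change.** - In 14.2.3, delete the sentence on random effects. State that the model has the listed fixed effects and one unstructured within-patient covariance over V2 to V9, fitted by REML with Kenward-Roger.
- Define the fallback as heterogeneous Toeplitz, without random visit effects, used only if the unstructured model fails to converge or gives a non-positive-definite covariance matrix or Hessian.
- In 14.2.4, state that one covariance structure is applied to all 200 imputed data sets.
- Confirm that the code in 17.4 agrees, and change it only if it does not.

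The cost is a few lines of SAP text and at most a line of code, with no new data and no effect on the primary analysis.

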#### 14.2.4 MMRM under MNAR

Each of the 200 imputed datasets created under MNAR condition as described in section 14.2.1, will be analyzed using the MMRM described in previous section 14.2.3 including all observed and imputed data. Rubin's rule will be used for combining results to draw inference.

Treatment group comparisons at each visit will be estimated by differences between least squares (LS) means from the visit by treatment interaction, with accompanying p-values and 95% CIs. The robustness of primary results will be evaluated by means of the difference of LS means at week 48.

#### 14.2.5 ANCOVA

The population-level summary for the variable will be altered. An ANCOVA model will be performed on the changes from baseline in FEV1 to Week 48, using the same stratification factors and the same covariates described for the LMM for the primary efficacy analysis (except for time factors). In case of death or re-transplantation events, FEV1 will be imputed as zero at each nominal day post event.

In case of violation of the normality assumption even after log transformation (section 14), then rank transformation will be applied to normalize the data. The same ANCOVA model will be applied to the rank-transformed data.

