## Sensitivity analyses

Intercurrent missing values and values missing due to death, re-transplantation and withdrawal of consent are assumed to be Missing At Random (MAR). Sensitivity analyses to the MAR assumption will be performed using different approaches, including selection modelling, simultaneous modelling of repeated FEV1 outcome and time to drop out, and controlled missing values imputation, and an analysis where re-transplantation and death are included in the definition of outcome variable and estimand as worst outcomes.

In addition to use of LMM to analyze the primary endpoint, simple t-test comparing the difference in mean FEV1 change from baseline to Week 48 between the treatment group in the FAS population including a 95% confidence interval for the treatment difference of the mean FEV1 change between the two treatment groups will be performed.

Further sensitivity analyses will be described in the SAP.

CCI

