# 8.3.4 Final decision on appropriateness of primary analysis: LMM vs. ANCOVA.

The recommendations from the blinded statistician (December 1st, 2021) have been evaluated

- to continue to strive to achieve the originally planned total patient number of 220 for both clinical trials combined (BOSTON-1 and BOSTON-2) and revise the BOSTON-2 protocol and the new sample size accordingly.
- to implement efforts to minimize missing data in both studies. In general, all patients who maintain consent to be followed for additional outcome information, including patients who discontinue study treatment, should remain in the study for all important safety and efficacy assessments for the full duration of the trial.
- to clearly pre-specify a primary analysis (the meeting package indicates that the primary analysis may be based on ANCOVA, if the LMM model is not viable at the end of the study, in light of the ongoing COVID-19 pandemic). Modifications to the analysis of the endpoints should be reflected in an updated statistical analysis plan before locking the database and prior to viewing any comparative analysis results.

Based on the above considerations, the LMM is deemed applicable, and it will be used for the primary analysis, while ANCOVA will be used as sensitivity analysis, in addition to sensitivity analyses assessing robustness on missingness mechanism and LMM.

Final Version 5.0 Page 25 of 76

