#### 14 EFFICACY

For the efficacy analysis, the adequacy of the model assumptions will be checked, and if it is found that these are inadequate then alternative approaches may be performed.

For all variables assumed to be normally distributed, the conditional studentized residuals from this model will be tested using the Shapiro-Wilk test. If the assumption of normality of these residuals is violated, then a log-transformed model will be fitted. The need for a possible log transformation of these variables will be investigated prior to unblinding by assessing the model residuals without a treatment term. Where data are transformed for analysis, back transformation will be applied for the presentation of results. Presentation of the tables will be amended as needed for this, with the addition of an explanatory footnote.

Classification and imputation of missing data will be completed prior to any transformation of the data for analysis.

As a general remark for all efficacy endpoints based on spirometry data, values collected at 1h and 4h post dose will not be used for any efficacy analyses as they are collected only for safety evaluations.

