#### 14.1 PRIMARY EFFICACY ANALYSIS

## 14.1.1 Analysis Population and Estimand

The primary endpoints will be analyzed using a "composite strategy" (International Conference on Harmonization (ICH) guideline E9 addendum on estimands and sensitivity analysis in clinical trials to the guideline on statistical principles for clinical trials). The estimand is defined by the following:

- Population: adult recipients of a double pulmonary allograft with clinically defined BOS, matching the inclusion and exclusion protocol criteria.
- Variable: FEV1 data at Week 48 (visit 9) collected from the onsite CO spirometer (data collected with the CO home spirometer will be used for supplementary analyses).
   Only accepted over-reader best FEV1 data for the session from CO will be used for analysis; data will not be re-derived.

Final Version 5.0 Page 38 of 76

Intercurrent events: After IEs such as stopping treatment with L-CsA, augmentation of SoC therapy, etc.,  $FEV_1$  measurements will still be collected and used in the analysis. In case of IEs preventing the use of  $FEV_1$  measurements, i.e. death and re-transplantation, the  $FEV_1$  will be imputed as treatment failure:  $FEV_1$  equal to zero for all visits subsequent the event.

Rejected spirometries are those that did not meet the American Thoracic Society criteria; if rejected, then they would be re-done but there may be cases where they are rejected twice and resulting in missing data. Rejected spirometry is not an indicator of a better/worse outcome and can be assumed to be MAR.

• Population-level summary: difference in mean change from baseline in the FEV1 at week 48 between treatment groups.

Table 5 summarizes the statistical approaches for handling IEs and missing data.

Final Version 5.0 Page 39 of 76

Table 5: Summary of strategies for Intercurrent Events and Missing data.

	Statistical analysis					
Type of IEs	Primary analysis (section 14.1.3)	Missing data not at random (MNAR) (section 14.2.1)	"While on treatment" strategy (for COVID-19) (section 14.3.3.3)	"While on treatment" strategy (section 14.3.5)	Trimmed Means (section 14.3.6)	
Death	The FEV 1 value will be	The FEV 1 value will be imputed equal to zero.	Not applicable.	Not applicable.	The FEV 1 value will be	

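### If normality fails, the ANCOVA sensitivity analysis switches to ranks: it then gives no mL estimate, and deaths and re-transplantations carry much less weight than in the composite mean difference it is meant to check

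*SAP*

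**What the plan says.** SAP 8.3.4 settles the primary model as the LMM, "while ANCOVA will be used as sensitivity analysis". Protocol 15.5 mentions power for the ANCOVA when it describes the benefit of the larger sample.

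SAP 14.1.1 adopts a composite strategy: after death or re-transplantation, FEV1 "will be imputed as treatment failure", that is, set to zero. SAP 14.2.5 carries this into the ANCOVA, where FEV1 "will be imputed as zero at each nominal day post event". A failure's change from baseline is therefore minus the baseline FEV1.

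The switch has two stages:

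- SAP 14 (opening paragraphs): residuals "will be tested using the Shapiro-Wilk test"; if normality is violated, "then a log-transformed model will be fitted". The need for a log is judged before unblinding, on residuals from a model without treatment. No significance level and no shift constant are given.
- SAP 14.2.5: "In case of violation of the normality assumption even after log transformation (section 14), then rank transformation will be applied to normalize the data". And then: "The same ANCOVA model will be applied to the rank-transformed data".

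Section 14.2.5 does not say whether the untransformed ANCOVA is still reported, and it names no effect measure for the ranked one.

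**The concern.** The primary estimand is a difference in mean change in which a failure costs the patient's whole baseline FEV1. A sensitivity analysis of that estimand should return the same quantity under other assumptions. On ranks, a failure costs only a low position in the ordering, and the treatment coefficient is a difference in adjusted mean rank. Section 14 asks for back-transformation of transformed data, but a rank difference cannot be turned back into mL. Ranks without ties are also uniform, so they do not normalize the data as the text intends.

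At stake is how the result is read. A ranked ANCOVA listed as a sensitivity analysis could be taken to confirm the primary finding when excess events on L-CsA have cancelled the mean benefit. It could also fail to show a benefit that consists of fewer events.

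**Working it through.** **Inputs from the documents.** SAP 8.2: 169 randomized, difference 200 mL, SD 350 mL. SAP 7.2: allocation 1:1. SAP 14.1.3: one-sided 0.025. SAP 14.2.5: zero coding.

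**Assumed, because the documents do not give them.** Baseline FEV1, number of events, survivor mean change (-0.1 L), and a Shapiro-Wilk level of 0.05. Protocol 15.2.3.1 says only that such events should be rare.

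**The plan's own figure.** With 50 per arm the noncentrality is 0.2/(0.35 × √(2/50)) = 2.857. Power is 80.8% at 50 per arm and 79.96% at 49, so 50 is reproduced. 100/(1 - 0.09) ≈ 110 total.

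**Step 1: the log step.** A log needs positive values. With SD 0.35 L, the share of survivors with change at or below zero is Φ(-m/0.35): 50% for mean change m = 0, 61% for -0.1 L and 80% for -0.3 L. Taking the log of FEV1 itself fails for every failure, because FEV1 is zero. Without a stated shift, the log step has no defined result.

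**Step 2: how often Shapiro-Wilk rejects.** 169 patients, baseline SD 0.5 L, residuals without treatment, 2,000 runs per setting:

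| Events in total | Baseline 1.2 L | 1.8 L | 2.5 L |
|---|---|---|---|
| 0 | – | 5% | – |
| 1 | 30% | 65% | 94% |
| 2 | – | 90% | 99.8% |
| 3 | – | 96% | – |
| 4 | 72% | 99% | – |
| 8 | 94% | over 99.8% | – |

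A dash means no figure is quoted. Removing 33% of the Week 48 values moves these by about 3 points at most. With random events and baseline 1.9 L (SD 0.6), rejection is 97-100% at event rates of 3% or more. At 3% and 1.2 L it is 69%.

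**Step 3: weight of one failure.** At baseline 1.8 L a failure lies about 4.7 survivor SDs below the survivor mean in mL, and 1.8 to 1.9 on ranks. 4.7/1.9 ≈ 2.5, so the weight is strongly reduced but not removed.

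**Step 4: effect on the conclusion.** Let p_A and p_B be the event rates on L-CsA and SoC, δ the survivor benefit, B the baseline and m the SoC survivor mean change. The composite mean difference is

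Δ = (1 - p_A)δ - (p_A - p_B)(B + m).

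With B = 1.9 and m = -0.1:

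- 10% v 5%, δ = 0.10: 0.90 × 0.10 - 0.05 × 1.8 = 0 mL
- 12% v 5%, δ = 0.15: 0.132 - 0.126 = 6 mL
- 5% v 12%, δ = 0: 0.07 × 1.8 = 126 mL

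Simulated one-sided significance (85 v 84 patients, survivor SD 0.35 L, baseline SD 0.6 L):

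| Events, L-CsA v SoC | Survivor benefit | mL ANCOVA | Ranked ANCOVA |
|---|---|---|---|
| 10% v 5% | 100 mL | 2.8% | 16.8% |
| 12% v 5% | 150 mL | 3.4% | 30.9% |
| 5% v 12% | none | 24.2% | 12.0% |

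With fixed counts, 200 mL in survivors and baseline 1.8 L (SD 0.5), 6 v 2 events cut the mL estimate from 199 to 106 (-47%) and the rank difference from 26.6 to 19.9 (-25%); significance is 19% v 77%. With 12 v 4 events the estimates are 17 mL (-92%) and 13.7 ranks (-49%); significance is 0.2% v 43%.

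**Step 5: validity.** With no survivor effect and equal event risk of 1%, 3%, 5% and 10%, one-sided error is 0.027, 0.026, 0.025 and 0.023 in mL, and 0.027, 0.025, 0.026 and 0.025 on ranks. Both hold their level.

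**The case against.** The ANCOVA does not decide the trial. Superiority rests on the LMM (SAP 14.1.3), and an excess of deaths on L-CsA would show there, in the MMRM, in the t-test and in the safety tables. The log decision is taken before unblinding. Section 14.2.5 opens by announcing that the population-level summary is altered. The scenarios above assume at least a twofold difference in event rates, which the documents do not suggest. The 16.8% and 30.9% are also not false positives, because survivors truly differ there. All of this stands and limits the consequence. What remains is that the altered summary is never named, and that the analysis is still listed as a sensitivity analysis of the primary endpoint.

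Four stronger readings are tempting but unsupported:

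- **Deaths hardly count on ranks.** They still take the lowest ranks, and with 12 v 4 events they halve the rank difference.
- **No mL estimate would remain.** This is true of the ANCOVA only. The LMM, MMRM and t-test (SAP 14.1.3, 14.2.3, 14.3.4) keep zero-coded mean differences, although the general log rule in section 14 could reach them too.
- **The switch is certain.** With one event, or a low baseline, it is not.
- **Ranking breaks a protocol rule on worst outcomes.** The protocol's phrase, "an analysis where re-transplantation and death are included in the definition of outcome variable and estimand as worst outcomes", describes a separate sensitivity analysis. A failure with a small baseline can rank above a survivor with a large loss, but that comes from the zero coding, which the mL ANCOVA shares. Tying failures at the worst rank left the first scenario at 16.8%.

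**Conclusion.** The point holds as a defect in one named sensitivity analysis. The log step is not computable as written. From about three events at a baseline near 1.8-1.9 L, the rank version would very likely be the only ANCOVA reported. It tests a different summary, without an effect size in mL. Under the assumed unequal event rates, its chance of significance is 6 to 9 times that of the mL ANCOVA when the composite mean difference is close to nil (16.8/2.8 and 30.9/3.4), and about half when the benefit lies wholly in fewer events (12.0/24.2).

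These sizes depend on event counts and baselines that the documents do not give. A reader might infer that the trial's conclusion, or its type I error, is at risk. Neither follows: the primary test is unaffected, and both ANCOVA versions hold their level under equal event risk. This is a cheap improvement to the SAP.

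**What to change.** Amend SAP 14.2.5, before database lock, so that:

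1. The untransformed ANCOVA is always reported, with its adjusted difference in mL and 95% CI.
2. If normality fails, inference uses a heteroscedasticity-robust standard error, or a permutation p-value stratified by the randomization factors (screening FEV1 class, age, region).
3. The log step is dropped for change scores.
4. The ranked ANCOVA, if kept, is an addition, labelled as a different estimand and given a named effect measure.

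The cost is a few sentences and one extra output. The mL test is also less powerful when events are balanced: in simulation, 62% v 89% for ranks at 5% events per arm and a 200 mL survivor benefit. That loss belongs to the composite mean itself.
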